1. BACKGROUND

In industrial countries worldwide and in Germany, glaucoma is the second most common cause of blindness. Glaucoma therapy with eye drops is the first line therapy. To achieve the target IOP (intraocular pressure) nearly half of the glaucoma patients require topical antiglaucomatous therapy with multiple drugs and different dosages. Therefore a consequent patient adherence is needed. With an adherence of only about 50% after one year of treatment, this is not sufficiently guaranteed. The resulting undertherapy may contribute to the progression of glaucoma damage. Therefore, surgical reduction of the intraocular pressure (IOP) is increasingly becoming an option for reducing topical therapy. The CyPass stent was developed as a less complicated surgical alternative to trabeculectomy.

We have been implanting the CyPass microstent at the Department of Ophthalmology in Neubrandenburg as a surgical glaucoma treatment procedure since 2009.

Since there is a negative pressure difference between the suprachoroidal space and the anterior chamber, the supraciliary CyPass microstent improves aqueous humor drainage into the suprachoroidal space.

In literature, we can only find follow-up data up to 2 years postoperatively for 'single' CyPass surgery [1, 2, and 3]. Long-term data are not yet available.

2. SYNOPSIS

2.1 Study objective

We designed this study to assess the long-term outcome after implantation of the supraciliary CyPass microstent beyond two years. The long-term results are of considerable importance for the evaluation and positioning of the CyPass stent procedure in the surgical glaucoma treatment armamentarium. We will collect data of a follow-up period of an average of 5 years.

The main research outcome is the determination of the efficacy of CyPass microstent implantation in reducing the intraocular pressure, the number of necessary antiglaucomatous medications and the progression of glaucoma in terms of visual field worsening and progression of glaucomatous optic disc changes.

Another main outcome is the safety of the procedure based on the intraoperative and postoperative complications.

Secondary outcomes include the development of the stent-associated blebs, the long-term success rate of the CyPass stent, and the clinical identification of stent failures.

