2.2 Study population

- We plan to examine at least 84 eyes. Therefore, we invite patients with at least 130 study eyes (see sample size calculation 2.7).
- All patients after implantation of a CyPass microstent on at least one eye. Excluded are patients which had combined operation (phacoemulsification with intraocular lens implantation and CyPass stent implantation)
- We will not invite the patients of whom we already have the long-term data available because they had been examined in the past at the department of Ophthalmology. We will take the available data from the medical records.
- Patients with secondary surgery due to CyPass failure will not be invited for the examination. We will collect the available data up to the date of the new operation from the patient's records and classify these cases as failure.

Protocol Version II 5-year CyPass results

- The following inclusion and exclusion criteria are considered for the prospective part of the study:

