2.3 Study design

Monocentric study with two parts:

- Retrospective part: Collection of preoperative, intraoperative and postoperative data from the medical records
- Prospective part: Inviting patients according to inclusion and exclusion criteria for a single examination and collection of postoperative data after an average of five years

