2.4 Study investigation plan

The pre- and intraoperative data, the data of the routine follow-up after 3 and 6 months postoperatively, as well as data of unscheduled examinations are taken retrospectively from the patient files.

- Collection of preoperative findings from the medical record:
 - i. Patient name, date of birth, gender, operated eye and surgery date
 - ii. General diseases and medications
 - iii. Eye diseases and already performed eye operations, if any
 - iv. Best corrected visual acuity
 - v. Topical and systemic glaucoma therapy and duration of glaucoma therapy
 - vi. Time of diagnosis of glaucoma, if available
 - vii. Intraocular pressure using Goldmann tonometer and time of measurement
 - viii. Central corneal thickness and pachymetric correction factor measured with the ultrasonic pachymeter or with Visante-OCT.
 - ix. Classification of the chamber angle width according to Shaffer classification
 - x. The lens condition or existing opacities of the natural lens or presence of an implanted intraocular lens at the time of surgery
 - xi. Visual field using Humphrey perimeter or TAP (Tuebinger automatic perimeter)
 - xii. Optic nerve configuration measured with the HRT-II (Heidelberg Retina Tomograph II)
 - xiii. Retinal nerve fiber layer thickness measured with Stratus OCT
- Collection of intraoperative characteristics or complications from the surgical report

Protocol Version II 5-year CyPass results

- Collection of available postoperative findings and complications
- A written or telephone invitation of the patients to a postoperative examination in the Department of Ophthalmology Neubrandenburg to collect the current, long-term postoperative findings
- The following examinations are performed during the study visit 5 years postoperatively:
 - i. Ophthalmic history
 - ii. Best corrected visual acuity
 - iii. Topical and possibly systemic glaucoma therapy
 - iv. Intraocular pressure using Goldmann tonometer
 - v. Central corneal thickness and the pachymetric correction factor measured with the ultrasonic pachymeter or with the Visante-OCT
 - vi. Visual field using Humphrey perimeter
 - vii. Gonioscopic findings
 - viii. The lens condition or opacities of the natural lens or of the implanted intraocular lens
 - ix. Optic nerve configuration measured with the HRT-II (Heidelberg Retina Tomograph II)
 - x. Nerve fiber thickness measured with Stratus OCT

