iv. *Visual field:* The visual field examination is performed by using the Humphrey Perimeter (Humphrey Field Analyzer, Model 720i, Carl Zeiss Meditec, Jena, Germany) with threshold test centrally 24-2. The visual field is evaluated with the help of the MD value and the PSD value. The rate of progression is expressed in the form of dB / year [8]. As a significant clinical change (improvement or worsening), MD values of ≥ 3 decibels are assessed [9]. In addition, the visual field defects in the central 5-degree visual field are counted in all four quadrants (4 visual field points in total) and evaluated as follows: points with sensitivity level > 10 dB are classified with 0 point, while the points with ≤ 10 dB are evaluated with 1 point. The points are added and then divided by 4. Thus, in the evaluation, the normal regular central visual field will be rated with 0 and the advanced central scotoma in all four quadrants is rated as 1.0.

v. *Glaucoma therapy:* Number and name of the active ingredients of the prescribed topical and systemic antiglaucomatous medications preoperatively and at follow-up visits are assessed. The duration of the postoperative drug-free phase is documented. The systemic intake of acetazolamide (carbonic anhydrase inhibitor) is documented separately and evaluated as absolute failure.

vi. *Visual acuity:* First, the refraction is measured with an auto refractometer (KR-800S, Topcon, Tokyo, Japan). The best-corrected visual acuity is checked and adjusted with the best possible correction using Snellen chart. For the statistical evaluation, a visual acuity of hand motion is documented as 1/800, light perception as 1/1600, and Nulla-lux as 1/3200 [10].

vii. *The optic disc change:* Pre- and postoperative optic disc measurement is performed using the HRT II (Heidelberg Retina Tomograph II, Heidelberg Engineering GmbH, Heidelberg, Germany). The area of the optic disc and

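### The main outcome includes efficacy in reducing glaucoma progression, but the plan specifies no comparator or preoperative rate, so it can describe progression after surgery but not show a reduction.

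*Combined protocol and SAP*

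**What the plan says.** Section 2.1 opens the main outcome with "The main research outcome is the determination of the efficacy of CyPass microstent implantation in reducing the intraocular pressure". The same sentence goes on to the number of medications and to "the progression of glaucoma in terms of visual field worsening and progression of glaucomatous optic disc changes". Read plainly, the verb *reducing* governs all three.

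Section 2.3 describes the design as "Monocentric study with two parts", a record review and a visit "for a single examination and collection of postoperative data after an average of five years". The population in section 2.2 is "All patients after implantation of a CyPass microstent on at least one eye", excluding combined cataract operations. No untreated, fellow-eye, historical or published comparison group is named there or in section 4.1.

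Section 2.4 lists the preoperative visual field (Humphrey or Tübingen perimeter), HRT-II and OCT among the findings to take from the record. It gives no number of examinations, no look-back period and no slope. At the study visit the field is by Humphrey only.

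For the field, section 4.5 says "The rate of progression is expressed in the form of dB / year [8" (the last characters open a literature citation) and treats an MD change of at least 3 dB, in either direction, as clinically significant. For the disc it says "Pre- and postoperative optic disc measurement is performed using the HRT II" and follows rim area and a segment score. Neither item gives a reference rate. Section 5 names the software but no test or model for progression.

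**The concern.** Pressure and drug count are levels, so each eye's preoperative value is a usable, though uncontrolled, comparator. A preoperative MD or rim area is also a level, but the outcome of interest is how fast that level changes. The change from the preoperative to the postoperative level is the postoperative progression itself. To say that it was reduced, one must know how fast the eye was changing before surgery, or how fast similar eyes change without the stent.

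Section 2.1 says that the results matter for placing the procedure among glaucoma operations. A mean rate reported under an efficacy objective would invite the reading that the stent slowed the disease, and the planned data cannot support that.

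**Working it through.** **The plan's own figures.** The plan gives no figure for progression. Its only calculation is the sample size in section 2.7: 21 × 8²/4² = 84, and 84/0.65 = 129.2, rounded up to 130. Both reproduce. The multiplier 21 equals 2 × (1.960 + 1.282)² = 21.01, which belongs to a comparison of two independent groups at two-sided 5% and 90% power. The plan has one group, so this calculation does not supply the missing comparator.

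**Can a change in rate be identified?** Change in rate = postoperative rate − reference rate. The plan specifies only the first term. Take an assumed postoperative rate of -0.5 dB/year:

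| Assumed preoperative rate (dB/year) | Change (dB/year) | Reading |
|---|---|---|
| -1.0 | +0.5 | halved |
| -0.5 | 0 | no effect |
| -0.25 | -0.25 | doubled |

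The same data fit all three rows. More eyes estimate the -0.5 more precisely and leave the choice of row open.

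**Does the 3 dB criterion help?** It counts change since an earlier field, and what it detects depends on follow-up. Section 2.1.1 (inclusion criteria) allows 3 to 8 years. Steady loss reaches 3 dB at 3/3 = 1.0 dB/year over 3 years, 3/5 = 0.6 over 5 years and 3/8 = 0.375 over 8 years. It provides no reference rate.

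**What can be described?** Assume the observed slopes have an SD of 0.5 to 2.0 dB/year (the documents give none) and treat 84 eyes as independent. The 95% half-width for the mean postoperative rate is 1.96 × SD/√84, that is 0.11 to 0.43 dB/year.

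**What could preoperative slopes add?** Assumptions, none from the documents: MD measurement SD 1.5 dB, 40 eyes with repeated preoperative fields, one postoperative field at five years, and the last preoperative field (y₀) shared by both slopes.

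- Three yearly preoperative fields (years -2, -1, 0). The preoperative slope is (y₀ − y₋₂)/2 and the postoperative slope is (y₅ − y₀)/5. In the difference the weights are 1/5 on y₅, −(1/5 + 1/2) on y₀ and 1/2 on y₋₂. The squared weights sum to 0.04 + 0.49 + 0.25 = 0.78. SE = 1.5 × √0.78/√40 = 0.21 dB/year; 95% half-width 1.96 × 0.21 = 0.41.
- Two preoperative fields one year apart. The squared weights sum to 0.04 + 1.44 + 1 = 2.48. SE = 1.5 × √2.48/√40 = 0.37 dB/year; 95% half-width 0.73.

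Both exclude true variation between eyes. The doubling row above is a difference of 0.25 dB/year, smaller than either half-width.

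**The case against.** The strongest reply is that this is long-term follow-up of an existing series. Section 2.1 begins by saying the aim is to assess long-term outcome, section 7 says the study is data collection and not an interventional trial, and section 4.5 treats field change in both directions without planning a test of slowing. On that view the mismatch is one of wording in a single sentence. Much of this stands. The lack of a control group is inherent in the design and is not the complaint, and the pre/post comparisons of pressure and medication remain usable. But the sentence does say *efficacy in reducing*, it is the main outcome, and the intention to describe should be what it states.

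A reader might also infer that the plan takes only one preoperative field per eye, or that dB/year is computed strictly from baseline to the study visit. The documents say neither. Section 2.4 gives no number of examinations and also draws on routine and unscheduled examinations from the files; section 4.5 states no interval. The files may well hold serial preoperative fields. What can be said is that no preoperative rate is specified.

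Finally, a reader might infer that a preoperative-slope comparison would settle the question. It would not. It is imprecise, as shown under the working. If worsening prompted surgery, regression to the mean would make the preoperative slopes look steep and favour the stent. Eyes with repeated fields may be a selected group. Mixing Humphrey and Tübingen fields could produce an apparent change of slope.

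**Conclusion.** The point holds for the progression part of the main outcome, for both visual field and optic disc. As specified, the plan can describe progression after surgery and cannot identify a reduction at any number of eyes. This conclusion rests on the design and needs no assumed value. The rates in the table are illustrations. The standard errors of 0.21 and 0.37 dB/year depend on the assumed 1.5 dB SD, 40 eyes and examination times. It does not follow that the study lacks value or that its pressure and medication outcomes fail.

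**What to change.** In section 2.1, keep *efficacy in reducing* for intraocular pressure and number of medications, and call these uncontrolled pre/post comparisons. Restate the progression part as: *to describe the postoperative rate of visual field change (dB/year, with confidence interval) and of optic disc change*. Add that no conclusion about reduction will be drawn.

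Optionally, and as exploratory only, extract all dated preoperative fields and HRT examinations on file in section 2.4 and compare preoperative with postoperative slopes within eye. Limit this to eyes with at least three preoperative fields on the perimeter used at the study visit (Humphrey). State with the result that regression to the mean and the selection of eyes with repeated fields may exaggerate apparent slowing.

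The required change is a line of text; its price is a narrower main objective. The optional analysis costs further chart extraction from files that are already being opened, and only part of the eyes would contribute.

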2.2 Study population

- We plan to examine at least 84 eyes. Therefore, we invite patients with at least 130 study eyes (see sample size calculation 2.7).
- All patients after implantation of a CyPass microstent on at least one eye. Excluded are patients which had combined operation (phacoemulsification with intraocular lens implantation and CyPass stent implantation)
- We will not invite the patients of whom we already have the long-term data available because they had been examined in the past at the department of Ophthalmology. We will take the available data from the medical records.
- Patients with secondary surgery due to CyPass failure will not be invited for the examination. We will collect the available data up to the date of the new operation from the patient's records and classify these cases as failure.

Protocol Version II 5-year CyPass results

- The following inclusion and exclusion criteria are considered for the prospective part of the study:

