2.6 Success of the treatment

We use two classifications to define treatment success:

- The first classification: dividing patients into 2 groups according to the need for postoperative glaucomatous medication: with and without medication. Then we divide each group into 4 subgroups according to the postoperative intraocular pressure achieved: patients with $IOP > 21\text{mmHg}$, patients with $IOP \leq 21\text{mmHg}$ and $> 18\text{mmHg}$, patients with $IOP \leq 18\text{mmHg}$ and $> 15\text{mmHg}$, and patients with $IOP \leq 15\text{mmHg}$.
- The second classification: definition of the treatment success according to the criteria of WGA (World Glaucoma Association) [4]. Complete success is achieved if the target IOP is reached without additional medication. Achieving the target pressure with additional local therapy is rated as qualified success. The loss of visual acuity to 'nulla lux' because of glaucoma progression, the need for systemic therapy with CAI (carbonic anhydrase inhibitor) to reduce pressure or the need for second glaucoma surgery are classified as complete failures.

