4.4 Documentation

The data will be collected first via a data collection form (Appendix 1) and then via the Excel program. We collect the intraoperative information from the surgical documentation books, the surgical reports and the patient medical records.

- Surgery-Date
- Patient Name, date of birth, gender and address of the patient
- Operated eye (OD/OS)
- Anesthesia
- Intraoperative course, peculiarities or complications
- Preoperative findings
- Postoperative findings

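### The do-not-invite rule for reoperated cases is written per patient although the sample is counted in eyes, so a non-reoperated stented fellow eye has no route to the study visit (minor)

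*Combined protocol and SAP*

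**What the plan says.** Section 2.2 sets the target in eyes: "We plan to examine at least 84 eyes", and "Therefore, we invite patients with at least 130 study eyes". It defines the population as "All patients after implantation of a CyPass microstent on at least one eye", combined procedures excepted, so a patient may contribute two study eyes.

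The rule for reoperated cases in the same section is worded by patient: "Patients with secondary surgery due to CyPass failure will not be invited for the examination". It continues: "We will collect the available data up to the date of the new operation from the patient's records and classify these cases as failure". Neither sentence is limited to the reoperated eye, and the word used for what is classified as failure is not defined as eye or patient.

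Elsewhere the unit is mixed. Section 2.6 sorts patients by pressure and medication, and states that "the need for second glaucoma surgery are classified as complete failures". Section 2.7 labels the same 84 and 130 as patients. Section 4.4 records which eye was operated on. Section 5 names no unit of analysis and does not say how two eyes of one patient are handled.

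**The concern.** Take a patient with a CyPass in both eyes, the right reoperated for failure and the left not. The left eye belongs to the population of section 2.2, but the patient is not invited, so that eye is not examined. Section 2.1 gives the purpose as outcome beyond two years. The routine file data named in section 2.4 are the 3- and 6-month visits plus unscheduled examinations. Without a visit, the left eye may therefore have no long-term pressure, visual field, optic disc or stent findings.

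The loss is tied to an outcome, namely failure in the same patient's other eye, so it could be informative. The undefined unit adds a second problem. Two analysts following the same text could end the left eye's data at different dates, or count its status differently.

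**Working it through.** **Plan's own figures.** Section 2.7: 21 × 8²/4² = 21 × 64/16 = 84. With a 65% response rate, 84/0.65 = 129.2, rounded up to 130. Both reproduce, and neither is affected by this point.

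**Reading the rule.** The target is in eyes, bilateral patients are admitted, and the bar on invitation applies to patients. The selection criteria in section 2.2 and the screening text in section 4.1 are also at patient level. No section provides a visit for a non-reoperated stented fellow eye. The missing visit is therefore the plain reading. The cut-off date and failure status of the fellow eye are ambiguous.

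**How many eyes.** The documents give no bilateral share, reoperation rate or between-eye correlation, so all three are assumed and varied:

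- b, share of eyes in bilaterally stented patients: 0.2 to 0.6
- f, reoperation rate per eye: 0.1 to 0.3
- ρ, correlation of reoperation between the two eyes: 0 to 0.5

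The share of eyes not reoperated but with a reoperated fellow eye is b × f × (1 − f) × (1 − ρ).

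- Lowest: 0.2 × 0.1 × 0.9 × 0.5 = 0.009, or 1.2 of 130 eyes
- Middle: 0.4 × 0.2 × 0.8 × 0.7 = 0.0448, or 5.8 of 130
- Highest: 0.6 × 0.3 × 0.7 × 1 = 0.126, or 16.4 of 130
- No bilateral patients (b = 0): none

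**What it does to the results.** This is a second illustration, again on assumed values: 130 eyes including 30 bilateral patients (60 eyes), reoperation rate p per eye, a bivariate normal model with latent correlation r between eyes, and half of the non-reoperated eyes counted as successes. Eyes without a visit = 60 × (p − P(both reoperated)). For p = 0.25 and r = 0, this is 60 × (0.25 − 0.0625) = 11.25.

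| p | r | Eyes without a visit | Success among them | Success, non-reoperated eyes, after dropping (from 50%) | Success, all eyes, before → after dropping | Reoperation-failure rate if scored as failures |
|---|---|---|---|---|---|---|
| 15% | 0 | 7.7 | 50% | 50.0% | 42.5 → 42.0% | 20.9% |
| 15% | 0.3 | 6.5 | 34% | 51.0% | 42.5 → 42.9% | 20.0% |
| 15% | 0.5 | 5.5 | 23% | 51.4% | 42.5 → 43.4% | 19.3% |
| 25% | 0 | 11.3 | 50% | 50.0% | 37.5 → 36.3% | 33.7% |
| 25% | 0.3 | 9.3 | 38% | 51.3% | 37.5 → 37.5% | 32.1% |
| 25% | 0.5 | 7.8 | 28% | 51.9% | 37.5 → 38.1% | 31.0% |
| 35% | 0 | 13.7 | 50% | 50.0% | 32.5 → 30.4% | 45.5% |
| 35% | 0.3 | 11.1 | 40% | 51.5% | 32.5 → 31.8% | 43.5% |
| 35% | 0.5 | 9.2 | 32% | 52.2% | 32.5 → 32.6% | 42.1% |

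Dropping the eyes moves success among non-reoperated eyes by 0 to 2.2 points. With reoperated eyes kept in the denominator as failures, as section 2.2 intends, overall success moves by −2.1 to +0.9 points. Scoring the fellow eyes as failures adds (eyes without a visit)/130, that is 4.3 to 10.5 points.

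In section 2.2 the 130 is the number of study eyes to invite, and reoperated patients lie outside it. Here it only sets the scale.

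**The case against.** The strongest defence is that the protocol uses the word patient loosely. The same 84 and 130 are eyes in section 2.2 and patients in section 2.7, and section 2.6 sorts patients by pressure, which is a property of an eye. The rule is tied to CyPass failure and stands under a target counted in eyes, so an investigator may well apply it per eye. This shows that a per-eye reading is available. It does not supply a visit for the fellow eye, because the sentence on invitations names patients and nothing qualifies it.

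The defence also limits how far the point can be taken:

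- A reader might infer that a functioning fellow eye will be scored as a failure or have its data cut at the other eye's operation. Section 2.6 ties complete failure to the need for a second glaucoma surgery, which that eye has not had. This reading is possible but strained.
- A reader might infer that the rule makes results look better. The table does not support a fixed direction: overall success falls at zero correlation for every reoperation rate, and also at 35% with correlation 0.3.
- A reader might pair the largest loss with the strongest selection. They do not occur together. The 13.7 eyes arise at zero correlation, where the lost eyes succeed as often as the rest.
- The eyes are not necessarily lost altogether. Section 2.4 collects available postoperative findings, including unscheduled examinations, from the files.
- A reader might extend the criticism to the bullet on patients with long-term data on file. Nothing there suggests that only one eye had been examined, so that extension is speculative.

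**Conclusion.** The point holds as a minor defect in the wording of section 2.2. A rule at patient level is applied to a sample counted in eyes. As written, it denies a study visit to an eligible fellow eye that has not been reoperated, and it leaves that eye's cut-off and status undefined.

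The size cannot be determined from the documents. On the assumed ranges, about 1 to 16 of 130 eyes are affected, in proportion to the unknown bilateral share. Under the second set of assumptions, simply omitting these eyes changes the success rate by about 2 points or less, with no fixed sign. Only the less natural reading, failure status for the whole patient, has a larger effect, about 4 to 10 points on the reoperation-failure rate. The documents do not support a claim of material or one-directional bias.

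**What to change.** Write the rule in section 2.2 per eye, for example: an eye with secondary surgery for CyPass failure is not examined in the study; its data are taken from the records up to the date of its own reoperation, and that eye is classified as failure. The patient is still invited if the other eye carries a CyPass, has not been reoperated and has no long-term data on file.

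The eye is already recorded under section 4.4, so no new data item is needed. The cost is a sentence or two of text and a few extra invitations to a visit that the study already runs.
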